8.10.1.1 Rescreening

Participants may be rescreened after initially failing to meet the inclusion/exclusion criteria. Results from assessments during the initial screening period are acceptable in lieu of a repeat screening test if performed within the specified time frame and the corresponding inclusion/exclusion criteria is met. Participants who are rescreened will retain their original screening number.

8.10.2 Treatment Period

Visit requirements are outlined in the SoA (Section 1.3). Assessments/procedures are to be performed prior to the administration of study intervention.

8.10.2.1 Phone Contact Visit

Telephone contact or visit on Cycle 1 Day 8 will be conducted to assess participants for development of early toxicity as outlined in the SoA (Section 1.3).

8.10.3 Posttreatment Visit

8.10.3.1 Safety Follow-up

Mandatory Safety Follow-up visits should be conducted approximately 30 days and 90 days after the last dose of study intervention or before the initiation of a new anticancer treatment, whichever comes first. If the EOT visit occurs approximately 30 days from last dose of study intervention, the 30-day Safety Follow-up visit is not required. In this situation, all procedures required at both the EOT visit and the 30-day Safety Follow-up visit should be performed at the EOT visit. End of treatment is defined as the date when the participant discontinues all study interventions.

If the 90-day Safety Follow-up visit falls within the same window as the imaging follow-up visit, these visits may be combined. All procedures required at the Safety Follow-up visit at 90 days will be performed at the imaging follow-up visit.

Participants who attain an investigator-determined confirmed complete response (CR) and stop study intervention with pembrolizumab + lenvatinib will have Safety Follow-up visits and move to follow-up per SoA (Section 1.3).

All AEs that occur prior to the Safety Follow-up visits should be recorded. Participants with an AE of Grade >1 will be followed until the resolution of the AE to Grade 0-1 or until the beginning of a new anticancer therapy, whichever occurs first. Serious AEs that occur within 120 days of the end of treatment or before initiation of a new anticancer treatment should also be followed and recorded.

8.10.3.2 Efficacy Follow-up Visits

Participants who complete the protocol-required cycles of study intervention or who discontinue study intervention for a reason other than disease progression will begin the

Efficacy Follow-up Phase and should be assessed approximately Q12W (or more frequently as needed) by clinic visit to monitor disease status; if a clinic visit is not feasible, the participant may be contacted by telephone or email. After Week 102, imaging should be performed Q24W. The Sponsor may request survival status to be assessed at additional time points during the study (not to exceed approximately 12 weeks). Every effort should be made to collect information regarding disease status until the start of new anticancer therapy, disease progression, death, end of study or if the participant begins retreatment with pembrolizumab as detailed in Section 6.6.4. Information regarding poststudy anticancer treatment will be collected if new treatment is initiated. Participants who complete all efficacy assessments and/or will not have further efficacy assessments must enter the Survival Follow-up Phase.

Participants who attain an investigator-determined confirmed CR and stop study intervention with pembrolizumab and lenvatinib will have Safety Follow-up visits and move to follow-up per SoA.

8.10.3.3 Survival Follow-up

Participant survival follow-up status will be assessed approximately Q12W to assess for survival status until death, withdrawal of consent, or the end of the study, whichever occurs first.

The first Survival Follow-up assessment should be scheduled as described below:

- For participants who discontinue study intervention and who will not enter the Efficacy Follow-up Phase, the first Survival Follow-up contact will be scheduled 12 weeks after the Discontinuation Visit and/or Safety Follow-up Visit (whichever is last).
- For participants who complete assessments in the Efficacy Follow-up Phase, the first Survival Follow-up contact will be scheduled 12 weeks after the last assessment in the Efficacy Follow-up Visit has been performed.

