		1			2				Cycle 3 Onwards ^a	Safety ^{b,c}	Efficacy Follow-up Visits ^d	
Visit Timing/Cycle Number	-28 to -1	1		2		Cycle 3 Onwards ^a		At DC	30 Days and 90 Days After Last Dose	Q12W	Q12W	All procedures and assessments are to be performed prior to administration of study intervention unless otherwise indicated. Refer to Section 8 for visit details.
Cycle Day		1	8	15	1	15	1					
Scheduling Window (Days)	-28 to -1		±3	±3	±3	±3	±3		+7	±7	±7	
												Imaging at EOT is not required if the previous tumor imaging assessment was within 4 weeks prior to the EOT visit. Imaging of any anatomy that shows disease either at screening or in subsequent evaluations will be required and should be submitted to the CIV.
Brain MRI ^e	X	↔					X			X		All imaging visits have a scheduling window of ±7 days. A brain MRI will be required at screening and at all subsequent tumor assessment time points only if brain disease was observed at screening or if clinically indicated. Imaging at EOT is not required if the previous tumor imaging assessment was within 4 weeks prior to the EOT visit.

Study Period	Screening	Treatment Cycle = 21 days						EOT ^b	Posttreatment Visits			Notes	
		1			2				Cycle 3 Onwards ^a	At DC	Safety ^{b,c}		Efficacy Follow-up Visits ^d
Visit Timing/Cycle Number	-28 to -1	1			2			Cycle 3 Onwards ^a	At DC	30 Days and 90 Days After Last Dose	Q12W	Q12W	All procedures and assessments are to be performed prior to administration of study intervention unless otherwise indicated. Refer to Section 8 for visit details.
Cycle Day		1	8	15	1	15	1						
Scheduling Window (Days)	-28 to -1		±3	±3	±3	±3	±3			+7	±7	±7	
Safety Procedures													
AE monitoring	X	X	X	X	X	X	X	X	X	X	X		AEs: monitored up to 90 days after last dose or 30 days following cessation of study intervention if the participant initiates new anticancer therapy, whichever is earlier. SAEs and pregnancy: monitored up to 120 days after last dose, or 30 days after last dose if participant starts a new anticancer therapy, whichever is sooner.
Full physical examination	X												To be performed within 7 days prior to start of study intervention.
Directed physical examination		X		X	X	X	X	X	X	X			In addition to the directed PEs in the flowchart, a symptom-directed PE may be performed at any time during the study, as clinically indicated.

Study Period	Screening	Treatment Cycle = 21 days						EOT ^b	Posttreatment Visits			Notes

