- a Participants who continue treatment with lenvatinib beyond ~2 years will follow the same SoA except for the following: 1) thyroid labs beyond ~2 years will be performed per SOC or as clinically indicated 2) Circulating tumor nucleic acids will no longer be collected. Participants who attain an investigator-determined CR and stop study intervention with pembrolizumab + lenvatinib will have Safety Follow-up visits and move to follow-up per SoA.

- b If EOT visit occurs ~30 days from last dose of study intervention, a Safety FU visit at 30 days is not required. In this situation, all procedures required at both the EOT visit and the Safety FU visit at 30 days should be performed. EOT will be defined as the date when the participant discontinues all study interventions.
- c Safety FU will occur during 2 separate visits: 30 days AND 90 days after last dose. If the 90-day Safety FU visit falls within the same window as the imaging FU visit, these visits may be combined. All procedures required at the Safety FU visit at 90 days will be performed at the imaging FU.
- d For participants who discontinue study intervention for reasons other than progressive disease, follow-up visits to monitor disease status continue until progressive disease or initiation of a new anticancer therapy. Participants who discontinue study intervention with progressive disease proceed directly to Survival Follow-up.
- e Brain MRI must be performed at Screening. Brain MRI should then be performed Q9W until Week 54 or sooner if clinically indicated; Q12W thereafter until Week 102; following Week 102, imaging should be performed every Q24W, or sooner if clinically indicated only for participants with brain disease present at Screening. Brain CT scan should only be used when MRI is contraindicated. The same imaging technique regarding modality and the use of contrast should be used in a participant throughout the trial to optimize the visualization of existing and new tumor burden.

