8.4 Adverse Events (AEs), Serious Adverse Events (SAEs), and Other Reportable Safety Events

The definitions of an AE or SAE, as well as the method of recording, evaluating, and assessing causality of AE and SAE and the procedures for completing and transmitting AE, SAE, and other reportable safety event reports can be found in Appendix 3.

Adverse events, SAEs, and other reportable safety events will be reported by the participant (or, when appropriate, by a caregiver, surrogate, or the participant's legally authorized representative).

The investigator and any designees are responsible for detecting, documenting, and reporting events that meet the definition of an AE or SAE as well as other reportable safety events. Investigators remain responsible for following up AE, SAEs, and other reportable safety events for outcome according to Section 8.4.3.

The investigator, who is a qualified physician, will assess events that meet the definition of an AE or SAE as well as other reportable safety events with respect to seriousness, intensity/toxicity and causality.

8.4.1 Time Period and Frequency for Collecting AE, SAE, and Other Reportable Safety Event Information

All AEs, SAEs, and other reportable safety events that occur after the consent form is signed but before treatment allocation/randomization must be reported by the investigator if the participant is receiving placebo run-in or other run-in treatment, if the event cause the participant to be excluded from the study or is the result of a protocol-specified intervention, including but not limited to washout or discontinuation of usual therapy, diet, or a procedure.

- All AEs from the time of treatment allocation/randomization through 90 days following cessation of study intervention or 30 days following cessation of study intervention if the participant initiates new anticancer therapy, whichever is earlier, must be reported by the investigator.
- All AEs meeting serious criteria, from the time of treatment allocation/randomization through 120 days following cessation of study intervention or 30 days following cessation of study intervention if the participant initiates new anticancer therapy, whichever is earlier, must be reported by the investigator.

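### For participants who go straight to Survival Follow-up without new anticancer therapy, SAE collection runs to day 120 but no contact is scheduled between the day-90 safety visit and about day 174

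*Combined protocol and SAP*

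**What the plan says.** **Length of the SAE window.** Section 8.4.1 requires reporting of "All AEs meeting serious criteria, from the time of treatment allocation/randomization through 120 days following cessation of study intervention", shortened to 30 days after cessation if new anticancer therapy starts. The Schedule of Activities (SoA, Section 1.3) agrees: "SAEs and pregnancy: monitored up to 120 days after last dose, or 30 days after last dose if participant starts a new anticancer therapy". Section 8.10.3.1 also uses 120 days.

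**Safety visits.** Section 8.10.3.1 states: "Mandatory Safety Follow-up visits should be conducted approximately 30 days and 90 days after the last dose of study intervention". SoA footnote c confirms that there are two such visits and no later one. The SoA window for them is +7 days.

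**Next contact.** Section 8.10.3.3 has two bullets. The first applies only to participants who will not enter Efficacy Follow-up; for them "the first Survival Follow-up contact will be scheduled 12 weeks after the Discontinuation Visit and/or Safety Follow-up Visit (whichever is last". The second covers participants who have been in Efficacy Follow-up and counts 12 weeks from their last efficacy assessment. SoA footnote d identifies the main group under the first bullet: "Participants who discontinue study intervention with progressive disease proceed directly to Survival Follow-up". The SoA window for Survival contacts is ±7 days.

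**The concern.** The protocol sets a 120-day SAE window but, for one group, schedules nothing that reaches its end. Section 8.4.2 makes open verbal questioning of the participant the preferred way of detecting events, and Section 8.4.3 ties active follow-up of reported events to later visits or contacts. Where no contact is planned, neither operates on schedule.

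The period matters. Section 6.6.1.1 says that immune-related events can appear several months after the last pembrolizumab dose. Safety is a secondary objective. Table 12 reports the proportions with a serious AE and with a drug-related serious AE, each with a 95% CI. Section 4.2 says the study could support regulatory approval. Table 8 starts the 24-hour reporting clock when the site learns of the event, so learning late means reporting late.

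**Working it through.** The plan states no figure for this gap, so there is none to reproduce. Days are counted from the last dose.

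**Inputs**
- SAE window: 120 days without new anticancer therapy (8.4.1, SoA, 8.10.3.1).
- Last safety visit: day 90, or up to day 97 with the +7 window (8.10.3.1, SoA).
- First Survival contact: 12 weeks, or 12 × 7 = 84 days, after the later of the discontinuation and safety visits, ±7 days (8.10.3.3, SoA).

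**Participants who do not enter Efficacy Follow-up**
- First Survival contact, nominal: 90 + 84 = day 174.
- Earliest: 90 + 84 − 7 = day 167. Latest: 97 + 84 + 7 = day 188.
- SAE days with no planned contact: 120 − 90 = 30, which is 30/120 = 25% of the window. If the safety visit is on day 97: 120 − 97 = 23, which is 23/120 = 19%.
- Delay from the close of the window to the next contact: 174 − 120 = 54 days nominal; 167 − 120 = 47 to 188 − 120 = 68 days with the windows.

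**Participants in Efficacy Follow-up**

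Section 8.10.3.2 has them assessed about every 12 weeks, but the anchor for the first assessment is not stated. Two assumptions bracket the possibilities.
- Counting 84 days from an end-of-treatment visit 0, 7, 14, 21 or 30 days after the last dose, the first assessment falls on day 84, 91, 98, 105 or 114. The first of these misses days 91 to 120; the other four fall inside.
- If contacts instead follow imaging counted from allocation (8.2.1.3), and the last dose falls at a random point in the imaging cycle, the chance of a scan in that 30-day stretch is 30/63 = 48% on the 9-week schedule, 30/84 = 36% on the 12-week schedule and 30/168 = 18% on the 24-week schedule.

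So a contact in days 91 to 120 is possible for this group but not guaranteed.

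**Participants who start new anticancer therapy**

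The SAE window shortens to 30 days after cessation (8.4.1), so the gap does not apply to them.

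**The case against.** The strongest reply is that the SAE obligation itself is intact and that several provisions soften the gap.

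- **Reporting to day 120 stays mandatory, and later reports count.** Section 8.4.1 also requires immediate reporting of any drug-related SAE that comes to the investigator's attention outside the window. This stands: no planned contact is not the same as no collection.
- **Survival contacts may already include AE questioning.** The AE-monitoring row of the SoA carries 11 marks, matching the 11 visit columns through Survival. The table is broken in the available text, so this is likely rather than certain. If it is right, the day-174 contact would recover some events, and what remains is delay and recall.
- **Other contacts exist.** Pregnancy testing runs to day 120, but only for women of childbearing potential and without a visit column of its own. Survival status may be requested at any time (SoA, 8.10.4), but that is optional and concerns survival only.
- **The group may be small.** Many who progress may start new therapy, which removes them. The documents give no proportion.

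A reader might also infer three stronger things that the documents do not support.

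1. That everyone lacks a contact until day 174. The 12-week rule counted from the safety visit is confined to those who skip Efficacy Follow-up. Participants who stop for toxicity without progression are normally outside it.
2. That the serious-AE rows of Table 12 are biased downward. This is not shown. Those rows count participants, so someone with an earlier SAE adds nothing, and late reports may still be captured.
3. That footnote d contradicts the mandatory safety visits. Its wording is best read as skipping Efficacy Follow-up. Section 8.10.3.3 times the Survival contact for this group from the safety visit, which presupposes that the visit takes place.

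**Conclusion.** A limited scheduling gap is established for participants who stop study intervention, do not enter Efficacy Follow-up and start no new anticancer therapy. For them the last 23 to 30 days of the 120-day SAE window have no planned contact, and the next one comes 47 to 68 days after the window closes. SAEs in that stretch may be under-ascertained or reported late.

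This rests on the safety visits taking place as scheduled and on the SoA windows. The number of participants and SAEs involved cannot be derived from the documents. For scale only, with about 100 participants, one missed SAE in a person with no other SAE would move the overall serious-AE proportion by 1/100, about 1 percentage point. The ORR, PFS, OS and DOR analyses and the sample size are untouched. This is an inexpensive improvement to safety ascertainment, not a flaw in the main analysis.

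**What to change.** In the first bullet of Section 8.10.3.3 and in the SoA, schedule the first Survival Follow-up telephone contact at about 120 days after the last dose for participants who skip Efficacy Follow-up and have not started new anticancer therapy. State that SAEs are asked about at that contact, and continue every 12 weeks from there (120 + 84 = day 204 for the next).

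For participants in Efficacy Follow-up who have not started new therapy, add an SAE telephone check at about day 120 only if no visit falls between day 91 and about day 120. Leave the second bullet of Section 8.10.3.3 unchanged.

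Optionally, reword SoA footnote d to say that Survival Follow-up comes after the Safety Follow-up visits. This clarifies the text and does not correct an error.

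Cost: for the first group, an existing call moves about 54 days earlier (174 − 120). Overall there is at most one extra call per participant, with no added clinic visit or procedure and no longer interval between survival contacts.

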8.10.4 Survival Status

To ensure current and complete survival data are available at the time of database locks, updated survival status may be requested during the study by the Sponsor. For example, updated survival status may be requested prior to but not limited to an external DMC review, interim and/or final analysis. Upon Sponsor notification, all participants who do not/will not have a scheduled study visit or study contact during the Sponsor-defined time period will be contacted for their survival status.

9 STATISTICAL ANALYSIS PLAN

This section outlines the statistical analysis strategy and procedures for the study. If, after the study has begun, changes are made to primary and/or key secondary objectives, or the statistical methods related to those objectives, then the protocol will be amended (consistent with ICH Guideline E-9). Changes to exploratory or other nonconfirmatory analyses made

after the protocol has been finalized, but prior to the conduct of any analysis, will be documented in a supplemental SAP (sSAP) and referenced in the Clinical Study Report for the study. A separate PK analysis plan as well as biomarker analysis plan may be provided. Post hoc exploratory analyses will be clearly identified in the Clinical Study Report.

Key elements of the statistical analysis plan are summarized below; the comprehensive plan is provided in Section 9.2 through Section 9.12.

9.1 Statistical Analysis Plan Summary

Study Design Overview	A Multicenter, Open-label, Phase 2 Trial to Assess the Efficacy and Safety of Lenvatinib (E7080/MK-7902) in Combination with Pembrolizumab (MK-3475) in Participants with Advanced Melanoma Previously Exposed to an Anti-PD-1/L1 Agent (LEAP-004)
Treatment Assignment	Approximately 100 participants will be enrolled to treatment with the combination of pembrolizumab and lenvatinib. This is an open-label study.
Analysis Populations	Efficacy and Safety: All Participants as Treated set (APaT)
Primary Endpoint(s)	OR as assessed by BICR per RECIST 1.1
Key Secondary Endpoint(s)	1. PFS as assessed by BICR per RECIST 1.1 2. OS 3. DOR as assessed by BICR per RECIST 1.1
Statistical Methods for Key Efficacy Analyses	Estimation of ORR; Estimation of PFS, OS, and DOR using the Kaplan-Meier method.
Statistical Methods for Key Safety Analyses	Counts and percentages of participants with AEs will be provided.
Interim Analyses	No efficacy interim analyses are planned. The external data monitoring committee (eDMC) will conduct regular safety monitoring.
Multiplicity	No multiplicity adjustment is planned.
Sample Size and Power	A sample size of approximately 100 is planned. Section 9.9 provides the precision of the ORR estimates.
Abbreviations: BICR = blinded independent central review; DOR = duration of response; ORR = objective response rate; OS = overall survival; PD-1 = programmed cell death protein 1; PFS = progression-free survival; RECIST 1.1 = Response Evaluation Criteria in Solid Tumors 1.1	

9.2 Responsibility for Analyses/In-house Blinding

The statistical analysis of the data obtained from this study will be the responsibility of the Clinical Biostatistics department of the Sponsor. This study is being conducted as a nonrandomized, open-label study, ie, participants, investigators, and Sponsor personnel will be aware of participant treatment assignments after each participant is enrolled and treatment is assigned.

9.3 Hypotheses/Estimation

There is no statistical hypothesis to be tested in this study. Objectives and endpoints of the study are stated in Section 3.

9.4 Analysis Endpoints

9.4.1 Efficacy Endpoints

9.4.1.1 Primary

- **Objective Response Rate (ORR) per RECIST 1.1 assessed by BICR**

Objective Response is defined as a best overall response of CR or PR. The details of the ORR analysis plan can be found in Section 9.6.1.1.

9.4.1.2 Secondary

- **Progression-free Survival (PFS) per RECIST 1.1 assessed by BICR**

PFS is defined as the time from the first day of study intervention to the first documented disease progression or death due to any cause, whichever occurs first. See Section 9.6.1.2 for definition of censoring.

- **Overall Survival (OS)**

OS is defined as the time from the first day of study intervention to death due to any cause. Participants without documented death at the time of the final analysis will be censored at the date of the last follow-up.

- **Duration of Response (DOR) per RECIST 1.1 assessed by BICR**

For participants who demonstrate CR or PR, DOR is defined as the time from first documented evidence of CR or PR until disease progression or death due to any cause, whichever occurs first. See Section 9.6.1.4 for definition of censoring.

